6.3 Handling of Missing Data

All attempts will be made to limit the amount of missing data. Unless otherwise specified, no attempt will be made to impute missing data. If a data point is missing, that data point will not contribute to that portion of the analysis.

6.4 Subject Disposition

A summary of subject disposition will be tabulated for all subjects by treatment group and overall, including:

- Number of screened patients
- Number of patients who failed screening
- Number of subjects enrolled
- Number of patients randomized
- Number of patients treated
- Number of patients who completed treatment
- Number of patients who discontinued treatment and the reasons for treatment discontinuation
- Number of patients who completed study
- Number of patients who discontinued study participation and the reasons for discontinuation from the study.

The number of patients included in each analysis population will also be summarized.

6.5 Demographics and Baseline Characteristics

Baseline characteristics will include standard demography (e.g., age, gender, ethnicity, race, weight, height, BMI), NYHA classification, smoking history, number of blocked vessels, and extent of coronary heart disease. Medical history will include information on pre-existing/prior AKI, cardiovascular disease, peripheral vascular disease, diabetes mellitus, hypertension, hyperlipidemia, obesity, prior TIA or stroke, etc.

| Statistical Analysis Plan | | Pa | ge 12 of 19 |
|---------------------------|---|----|-------------|
| Sponsor | Study | | Version |
| CytoSorbents | rbents CytoSorb [®] REduction of FREe Hemoglobin/Acute Kidney Injury (AKI) during Cardiac Surgery | | 1.0 |

Demographic and baseline characteristics will be summarized for the ITT population using descriptive statistics for each treatment group and overall, with Roll-in subjects presented in parallel.

Medical history by MedDRA system organ class (SOC) and preferred name will be summarized by treatment group and overall. For each subject, multiple medical histories of the same MedDRA SOC or preferred name will be counted only once within each MedDRA SOC and preferred name. Medical histories will be sorted alphabetically by MedDRA SOC and preferred name.

Previous procedure will be summarized as the number and percentage of subjects by procedure category, treatment group and overall, with Roll-in subjects presented in parallel.

6.6 Procedural Data

Procedural data will include procedure type, valves involved, number of grafts, valve involvement, evidence of cerebral perfusion and type (if applicable), hemoconcentrator use, heparin use, lowest core body temperature, and procedural durations (i.e., total operative time, total CPB time, cross clamp duration, etc.).

Data will be summarized for the ITT, and safety population using descriptive statistics for each treatment group and overall, with Roll-in subjects presented in parallel.

6.7 Analysis of Study Endpoints

6.7.1 Primary Efficacy Endpoints

The primary effectiveness endpoint is the incidence or severity of AKI (i.e., incidence of AKI and proportion of AKI by stage) in the first 48 hours after surgery when used intraoperatively with cardiopulmonary bypass (CPB) in subjects undergoing cardiac surgery as defined by the KDIGO clinical practice guideline through 48 hours post-cardiac surgery.

6.7.1.1 Primary Analysis

AKI severity (stage 0, 1, 2, 3) based on creatinine measured at CPB, 24-hours post-CPB, and 48-hours post-CPB will be summarized using descriptive statistics. Summaries will be provided for the ITT and Roll-ins. Data will be displayed by treatment group and overall, with Roll-ins presented in parallel. AKI stage is based on the 'worst' criteria being met and subjects included in each severity level will be mutually exclusive across levels.

The number and proportion of subjects will be given for the following severity breakdowns:

CytoSorbents

| Statistical Analysis Plan | | Pag | ge 13 of 19 |
|---------------------------|--|-----|-------------|
| Sponsor | Study | | Version |
| CytoSorbents | Ents CytoSorb [®] REduction of FREe Hemoglobin/Acute Kidney Injury (AKI) during Cardiac Surgery | | 1.0 |

- Stage 0 (no AKI)
- Stage 1 (mild AKI)
 - \circ Serum creatinine increase of 1.5-1.9 times baseline, or
 - Serum creatinine increase of ≥0.3mg/dL over baseline, or
 - urine output < 0.5 mL/kg/h for 6 h
- Stage 2 (moderate AKI)
 - o Serum creatinine increase of 2.0-2.9 times baseline, or
 - urine output < 0.5 mL/kg/h for ≥ 12 h
- Stage 3 (severe AKI)
 - Serum creatinine ≥3 times baseline, or
 - Serum creatinine increase to ≥4.0mg/dL, or
 - Initiation of renal replacement therapy, or
 - urine output < 0.3 mL/kg/h for ≥ 24 h, or
 - anuria for ≥ 12 h
- Stage 1, 2, or 3
- Not reported

Comparisons between SoC and SoC+CytoSorb[®] will be made using Fisher's exact tests. Statistical comparisons will be done for the ITT population only.

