### 11.1.2 Effectiveness evaluations:

The primary endpoint will be assessed in each modified intent-to-treat (mITT) population in step-wise fashion beginning with the primary sub-population. If a significant beneficial effect is met for CytoSorb over control at a one-sided overall 0.025 level of significance, then the study will be considered to be a primary endpoint statistical success on this subpopulation and testing will proceed to the secondary sub-population. Otherwise the study will be considered to have statistically failed the primary endpoint.

We have selected to use a modified intent-to-treat population (mITT) population to avoid the consequence of including patients that were excluded from the study after randomization due to administrative reasons.

Use of the mITT population as defined is not anticipated to result in bias or informative censoring of the data.

The primary endpoint (rank order presence and severity of AKI) will be compared between treatments with Wilcoxon Rank Sum test. Continuous endpoints will be assessed via ANCOVA with baseline value as covariate. Binary endpoints will be assessed via unconditional exact binomial test. The primary endpoint will be summarized by subgroup factors, e.g., those who receive IV contrast within 48 hours prior to surgery versus those who do not. Additionally, subgroup-by-treatment interaction may be tested via generalized ordered categorical model and/or for binary combinations of outcomes (e.g., presence / absence of any AKI, and/or severe AKI) by logistic regression. Details will be in the SAP.

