### 11.2 Statistical Power and Sample Size Determination

The REFRESH II study hypothesis is that, for patients at increased risk for AKI based upon use of the Cleveland Clinic Score for stratification of the risk of cardiac surgery associated AKI (CSA-AKI), the intra-operative usage of the CytoSorb device in addition to the standard of care in a bypass circuit during cardiopulmonary bypass will decrease the overall incidence and/or proportion of acute kidney injury (AKI) by stage as defined by the Kidney Disease Improving Global Outcomes (KDIGO) clinical practice guideline definition of acute kidney injury. The AKI Stage is scored as 0, 1, 2 or 3. AKI Stage of 0 indicates no AKI, and AKI stages 1, 2 and 3 indicate mild, moderate, and severe AKI, respectively. Success will be defined by demonstrating a shift in distribution toward overall less severe AKI or fewer incidences of AKI in the CytoSorb population.

The distribution of AKI Stage (0, 1, 2, 3) expected in the control group was estimated from prior data. Sample trial outcomes for which power was computed are summarized in **Error! Reference s ource not found.** below for total N=267 patients in the primary analysis subgroup ("without HCA", randomized 1:1). The proportion of "without HCA" patients will be at least 2/3 of the total sample size 400. 420 patients will be enrolled to account for an expected 5% premature withdrawal rate. Power was computed for comparing binomial proportions of patients with AKI Stage 1, 2, or 3 (or i.e., any AKI); proportions with AKI Stage 2 or 3; and for an ordered categorical rank test comparing the distribution of AKI Stages 0, 1, 2, 3 between treatments. Since it is uncertain whether CytoSorb will lower the overall AKI rate or that of Stages 2 and 3, the ordered categorical test will be primary, i.e., the primary null and alternative hypotheses are

- H0:  $\pi 00 = \pi 01$ ,  $\pi 10 = \pi 11$ ,  $\pi 20 = \pi 21$ ,  $\pi 30 = \pi 31$
- H1:  $\{\pi 30 \ge \pi 31 \text{ and/or } (\pi 20 + \pi 30) \ge (\pi 21 + \pi 31) \text{ and/or } (\pi 10 + \pi 20 + \pi 30) \ge (\pi 11 + \pi 21 + \pi 31)\}$  AND one or more of the above is strictly ">"

where  $\pi i0$  is the proportion of control patients in AKI level i (i=0, 1, 2 and 3) and where  $\pi i1$  is the proportion of CytoSorb patients in level i. Note that level i=0 is no AKI. The test of the null

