### 11.2.1 Interim Analyses

Specifically, since the treatment difference could be larger or smaller than expected, interim analyses will be carried out for potential (NON-BINDING) early stopping for an efficacy or futility conclusion.

Note that the BLINDED combined AKI incidence rate will be monitored throughout the trial to inform on enrichment with patients at higher risk of AKI so as to yield sufficient AKI events to improve the expected precision of the treatment comparison.

Table 5: Overall Power for the ordinal outcome, the Any AKI dichotomous outcome (labeled Stages 1,2,3 below), and the Moderate/Severe AKI dichotomous outcome (labeled Stages 2,3 below).

		Р	ercent of	Patients	with Ind	icated AKI Sta	ge
Al	KI Stage>	0= no AKI	Stage 1	Stage 2	Stage 3	Stages 1,2,3	Stages 2,3
Example 1	CytoSorb	36%	53%	10%	1%	64%	11%
N=267	Control**	24%	47%	26%	3%	76%	29%
	power*>		0.9	0.57	0.96		
Example 2	CytoSorb	44%	40%	14%	2%	56%	16%
(total N=267)	Control**	24%	47%	26%	3%	76%	29%
	power*>		0.9	0.94	0.72		
* power to y with total N	ield statistical "without HCA	ly significa \" patients 1	nt (alpha= andomize	0.025 1-s	sided) dif	ference between	treatments

Note that the dichotomous outcomes will be considered secondary. The Table 5 power calculations do not consider the planned interim analyses. They are presented for reference, and to demonstrate the rationale for the primary analysis method based on the ordinal outcome. Note that for example 1, had the primary endpoint been the dichotomous outcome any AKI, power would have been only 57%. For example, 2, had the primary endpoint been the dichotomous outcome moderate/severe AKI, power would have been only 72%. For both examples 1 and 2, power is over 90% via the ordinal outcome.

Simulations were carried out for a Group Sequential Design (GSD) planned for Total N=267 "without HCA" patients (randomized 1:1), with Interim Analyses (IA) after AKI status (Stage 0,1,2,3) is determined for 138 (IA1 at  $\frac{1}{2}$  total N) and N=200 (IA2 at  $\frac{3}{4}$  total N). NON-BINDING early stopping for efficacy is considered if p<0.001 at IA1 or IA2; and NON-BINDING early futility stopping is considered if the Conditional Power (CP) is less than 5%. The final analysis requires p<0.0247 1-sided in order to control the overall type 1 error at 0.025 1-sided.

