### 11.3 Study Success

An individual study subject will be defined as a success if during the 48 hours following surgery, they do not receive a diagnosis of AKI by the KDIGO Guidelines. In contrast, a patient whose clinical parameters result in a diagnosis of AKI will be classified according to AKI stage. Study success will be defined by demonstration of a statistically significant shift in distribution of AKI Stages 0, 1, 2, 3 toward less severe and/or no AKI with CytoSorb in comparison to standard of care.

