4.1 Study Design Changes

The study was stopped early at the discretion of the sponsor, prior to any interim analyses being performed. Total enrollment, including roll-ins reached 151 subjects of the planned 420. Analyses described within this SAP reflect those that will be performed for the final report that includes results

| Statistical Analysis Plan | | Ра | ge 9 of 19 |
|---------------------------|---|----|------------|
| Sponsor | Study | | Version |
| CytoSorbents | ts CytoSorb [®] REduction of FREe Hemoglobin/Acute Kidney Injury (AKI) during Cardiac Surgery | | 1.0 |

from the 151 patients and may not reflect those originally planned for the total study population as stated in the CIP.

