4.3 Blinding

See Section 3.6 of the CIP for additional details on Maintaining the Study Blind and Unblinding Procedures.

5 Sample Size Determination

The REFRESH II study hypothesis is that, for patients at increased risk for AKI based upon use of the Cleveland Clinic Score for stratification of the risk of cardiac surgery associated AKI (CSA-AKI), the intraoperative usage of the CytoSorb^{*} device in addition to the standard of care in a bypass circuit during cardiopulmonary bypass will decrease the overall incidence and/or proportion of acute kidney injury (AKI) by stage as defined by the Kidney Disease Improving Global Outcomes (KDIGO) clinical practice guideline definition of acute kidney injury. The AKI Stage is scored as 0, 1, 2 or 3. AKI Stage of 0 indicates no AKI, and AKI stages 1, 2 and 3 indicate mild, moderate, and severe AKI, respectively. Success will be defined by demonstrating a shift in distribution toward overall less severe AKI or fewer incidences of AKI in the CytoSorb^{*} population. For full explanation of sample size determination, refer to 2017-001, Version F section 11.2.

6 Statistical Analyses

| Statistical Analysis Plan | | Pa | ge 10 of 19 |
|---------------------------|--|----|-------------|
| Sponsor | Study | L | Version |
| CytoSorbents | CYTOSORB [®] REDUCTION OF FREE HEMOGLOBIN/ACUTE KIDNEY INJURY (AKI) DURING CARDIAC SURGERY | | 1.0 |

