6.1.4 Statistical Significance

Unless otherwise specified, hypothesis testing will be performed at the two-sided 0.05 significance level. P-values will be rounded to three decimal places. If a p-value is less than 0.001 it will be reported as "<0.001". If a p-value is greater than 0.999, it will be reported as ">0.999".

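### The SAP replaces the protocol's ordinal Wilcoxon test of AKI stage with unspecified Fisher's exact tests, without a reason, while keeping a success definition based on a shift in stage

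*SAP*

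**What the plan says.** Protocol 11.1.2: "The primary endpoint (rank order presence and severity of AKI) will be compared between treatments with Wilcoxon Rank Sum test". Protocol 11.2 gives the reason. It is not known whether the device would lower AKI overall or only Stages 2 and 3, so "the ordered categorical test will be primary, i.e., the primary null and alternative hypotheses are" those on the full stage distribution, tested one-sided at 0.025. The text under Table 5 (Protocol 11.2.1) makes the dichotomies secondary and shows what each would have cost: for Example 1, "had the primary endpoint been the dichotomous outcome any AKI, power would have been only 57" per cent. Protocol 11.3: "Study success will be defined by demonstration of a statistically significant shift in distribution of AKI Stages 0, 1, 2, 3" in the favourable direction.

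SAP 6.7.1.1, headed as the primary analysis, lists Stages 0, 1, 2 and 3, a combined Stage 1–3 row and a row for unreported values. It refers to creatinine at CPB, 24 hours and 48 hours. It then says comparisons "will be made using Fisher's exact tests", in the ITT population only. SAP 6.1.4 sets the default: "hypothesis testing will be performed at the two-sided 0.05 significance level".

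SAP section 5 keeps the protocol's criterion: "Success will be defined by demonstrating a shift in distribution toward overall less severe AKI or fewer incidences of AKI". SAP 4.1 discloses the early stop and warns that analyses "may not reflect those originally planned for the total study population as stated in the CIP". It says nothing about the change of test.

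**The concern.** The ordinal test was a deliberate choice. It protects power whichever part of the stage distribution moves, and it has a direction. The replacement can be read in at least two ways, and each has a defect.

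- **One 2×4 Fisher test.** It treats the four stages as unordered labels. A significant result says that the distributions differ, not that CytoSorb patients have lower stages.
- **Separate 2×2 tests by row.** Each is run at two-sided 0.05, with none named as primary and no multiplicity rule.

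The text also does not say whether testing is done once, on the worst stage, or at each listed time point. Two analysts could therefore run different primary tests from the same SAP, and the table could be chosen after the results are known. SAP 6.9 reports results by HCA only as binary odds ratios. No ordinal result is planned for the without-HCA patients, who were the protocol's primary population.

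**Working it through.** **Inputs.** Stage distributions (0/1/2/3) from Protocol Table 5: control 24/47/26/3%; CytoSorb 36/53/10/1% (Example 1) and 44/40/14/2% (Example 2). SAP 4.1 gives 151 enrolled including roll-ins, and the Protocol synopsis allows up to 80 roll-ins. The randomised number is not stated. I assume 35 to 75 per arm, from (151 − 80)/2 ≈ 35 and 151/2 ≈ 75.

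**Reproducing Table 5 (N = 267, one-sided 0.025).** The two-proportion formula gives 0.572, 0.936, 0.961 and 0.723, against the printed 0.57, 0.94, 0.96 and 0.72. For the ordinal test:

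- θ = P(CytoSorb stage lower) + ½P(tie)
- τ = 1 − Σp̄³, where p̄ is the pooled stage proportion
- power = Φ((θ − 0.5)√(3N/τ) − 1.96)

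Example 1: θ = 0.36×0.88 + 0.53×0.525 + 0.10×0.16 + 0.01×0.015 = 0.6112 and τ = 0.8422. Power = Φ(0.1112×√(801/0.8422) − 1.96) = Φ(1.47) = 0.93.

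Example 2: θ = 0.6199 and τ = 0.8704. Power = Φ(1.68) = 0.95.

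Both agree with the protocol's statement that ordinal power exceeds 90%.

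**Power at the assumed size, two-sided 0.05.** Wilcoxon (tie-corrected) and 2×4 Fisher (full enumeration) are from 15,000 simulated tables per setting. The 2×2 Fisher figures sum exact binomial probabilities over tables with p ≤ 0.05.

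| Example | Per arm | Wilcoxon | 2×4 Fisher | Any-AKI Fisher |
|---|---|---|---|---|
| 1 | 35 | 0.42 | 0.36 | 0.13 |
| 1 | 50 | 0.56 | 0.50 | 0.20 |
| 1 | 75 | 0.73 | 0.70 | 0.30 |
| 2 | 35 | 0.47 | 0.36 | 0.34 |
| 2 | 50 | 0.61 | 0.49 | 0.48 |
| 2 | 75 | 0.79 | 0.67 | 0.68 |

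The 2×4 test loses 3–6 points in Example 1 and 11–12 in Example 2. A Stage 2–3 Fisher test, which SAP 6.7.1.1 does not list, has 0.74 in Example 1 at 75 per arm but only 0.18 to 0.41 in Example 2 across 35 to 75 per arm.

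**Total N for 80% power.** Wilcoxon: (1.96 + 0.8416)²τ/[3(θ − 0.5)²] gives about 178 (Example 1) and 158 (Example 2). An unordered 3-df test (non-central chi-square) needs 201 and 213.

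**Order and direction under the 2×4 reading.** Take counts 20/38/15/2 (CytoSorb) and 18/30/24/4 (control). Permuting the stage labels leaves the 2×4 p-value at 0.289, while the one-sided Wilcoxon p moves from 0.07 to 0.89.

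As a constructed example, let the treated distribution be 10/75/12/3%. Mean stage is 0.75 + 2×0.12 + 3×0.03 = 1.08, the same as control (0.47 + 2×0.26 + 3×0.03 = 1.08). The 2×4 test rejects in 58%, 75% and 90% of trials at 35, 50 and 75 per arm, and the two-sided Wilcoxon in 5–6%. The distributions do differ here, so this is not type 1 error. It shows that a significant result need not mean a shift.

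**False positives under the row-wise reading.** The Stage 0 row and the Stage 1–3 row give the same 2×2 test, so there are four distinct tests per time point. Simulated under three null distributions (control, and control pooled with each example), the chance of at least one p ≤ 0.05 is 6.4% to 9.8% with equal arms and about 11% at 75/76.

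**The case against.** The best defence has five parts.

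- **The SAP discloses the change in general terms.** It was written after an early stop and says its analyses may differ from the protocol. That is true, but a smaller sample is no reason to drop stage order. The rank test needs no interim analysis or extra data and works at this size.
- **Row-wise 2×2 tests are the more natural reading.** SAP 6.7.1 describes the endpoint as AKI incidence and the proportion at each stage, and the next section lists those rows. I accept this. That reading still has no deciding test.
- **The success criterion has two limbs.** A 2×2 test of any AKI would address the incidence limb directly, and reported proportions would show direction. That is also fair, but the SAP does not say that this test decides. It is also the comparison with the 57% power that the protocol gave for not relying on it.
- **Fisher is not always weaker.** With one extra patient in an arm, 2×2 Fisher power can rise by up to about 9 points because of discreteness. The Stage 2–3 test reaches 0.79 in Example 1 at 75/76, slightly above Wilcoxon. The 2×2 figures are therefore approximate, and power loss is not the main argument.
- **The trial is underpowered under any test.** Wilcoxon itself reaches only 0.42 to 0.79. This limits what the result can show, but it is no reason to leave the primary test undefined.

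**Conclusion.** The concern holds and should be fixed before the analysis is run. The SAP replaces a justified ordinal primary test with one that cannot be carried out from the text, gives no reason specific to the test, and keeps a success definition that the replacement does not clearly serve.

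The main fault is the undefined test and the loss of order and direction. The power loss under the 2×4 reading is modest, and the row-wise false-positive rate is only moderately above 5%. The choice of table matters more: at 75 per arm in Example 1, any-AKI and Stage 2–3 Fisher tests differ by about 44 points (0.30 against 0.74).

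The figures rest on two assumptions: 35 to 75 randomised per arm, and Table 5 rates, which the protocol gives for without-HCA patients, applied to the whole ITT population. The specification gap depends on neither.

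**What to change.** Amend SAP 6.7.1.1 (SAP section 7 provides for this) as follows.

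1. Name one primary test: Wilcoxon rank-sum on each subject's worst AKI stage (0–3) through 48 hours, ITT population, two-sided 0.05.
2. State that this differs from the protocol's one-sided, stepwise test in the mITT sub-populations, and why.
3. Report a common odds ratio, or the probability of a lower stage, with a 95% confidence interval. State how unreported stages are handled.
4. Label Fisher's tests (any AKI, and Stage 2–3 if added) as secondary, with the table and time point given.
5. Show the ordinal result in without-HCA patients as supportive. If they are two-thirds of those randomised (24 to 50 per arm, assumed), power is only about 0.31–0.56 (Example 1) or 0.33–0.61 (Example 2).

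Stratifying the rank test by intended HCA (van Elteren) is an optional refinement, not a restoration of the protocol's test. If Fisher is kept as primary, the SAP must state the table, the time point and the reason.

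The cost is SAP wording and a few lines of SAS or R. No new data are needed.

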4.2 Randomization

Subjects will be randomized prior to the start of CPB surgery (within 5 business days prior to and including day of procedure), but only after the subject provides written informed consent and subject eligibility criteria is confirmed. Randomization will be stratified by study center and intended use of HCA as a surgical technique during the procedure, with a 1:1 allocation ratio (SoC+CytoSorb[®]:SoC alone). Randomized treatment will be assigned from the electronic database.

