6.9 Subgroup Analyses

Primary efficacy will be summarized for the following subgroups: HCA (Y/N), IV contrast within 48hrs prior to surgery (Y/N), biological sex (M/F), age (Age<65, Age \geq 65), baseline diabetes mellitus (Y/N), baseline heart failure (Y/N), and baseline hypertension (Y/N).

The outcome of interest will be AKI severity of 0 versus AKI severity of 1/2/3 at 48 hours. Logistic regression will be used to determine the odds ratio for SoC+ CytoSorb versus SoC within each subgroup. The odds ratio and associated 95% confidence intervals for each subgroup will be presented in a forest plot. The analysis will be repeated but with the outcome being AKI severity of 0 or 1 versus AKI severity of 2 or 3.

Analyses will be performed in the ITT population (excluding Roll-ins). These analyses are intended to demonstrate consistency of results across subgroups.

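### SAP 6.7.1.1 pre-specifies no overall effect estimate, no 95% confidence interval and no adjustment for the primary comparison of a trial that stopped well short of its planned size

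*SAP*

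**What the plan says.** SAP 6.7.1.1 first plans a table: "The number and proportion of subjects will be given for the following severity breakdowns", namely Stages 0, 1, 2 and 3, any stage combined, and not reported. Comparisons between arms, in the ITT population only, "will be made using Fisher's exact tests". The section names no effect measure, interval, model or covariate.

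SAP 6.9 does plan estimates, within subgroup levels. "Primary efficacy will be summarized for the following subgroups: HCA (Y/N") and six further factors. "Logistic regression will be used to determine the odds ratio for SoC+ CytoSorb versus SoC within each subgroup", on any AKI and again on Stage 2–3. "The odds ratio and associated 95% confidence intervals for each subgroup will be presented in a forest plot". The stated purpose is to show consistency across subgroups.

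On design, SAP 4.2 says: "Randomization will be stratified by study center and intended use of HCA". On size, SAP 4.1 says: "Total enrollment, including roll-ins reached 151 subjects of the planned 420".

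Protocol 11.1.2 and 11.2 planned an unadjusted Wilcoxon test and also name no effect estimate for the primary endpoint. For other outcomes, Protocol 11.1.2 says: "Continuous endpoints will be assessed via ANCOVA with baseline value as covariate".

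**The concern.** The report would show intervals for slices of the trial but none for the whole, so the subgroup forest plot has no overall estimate against which to judge consistency.

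Early stopping makes this matter more. A p-value above 0.05 from a sample well below plan is compatible both with no effect and with an effect of the size in Protocol Table 5. An estimate with an interval shows which effects remain plausible. Leaving it unspecified also leaves the effect measure, interval method and adjustment to be chosen after the results are known.

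The lack of adjustment is a smaller, separate matter of precision. Intended HCA is a stratification factor, and eGFR and creatinine are collected before surgery (Protocol 8.4, 8.5.2). The primary comparison uses neither intended HCA nor baseline renal function as a covariate.

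**Working it through.** **Inputs**
- Table 5 any AKI: control 76%; CytoSorb 64% (Example 1) or 56% (Example 2).
- Table 5 Stage 2–3: control 29%; CytoSorb 11% (Example 1) or 16% (Example 2).
- Table 5 size: 267 patients without HCA, 1:1, one-sided 0.025 (Protocol 11.2).
- SAP 6.1.4: two-sided 0.05.
- Enrolled: 151 including roll-ins (SAP 4.1). Roll-ins: up to 80 (Protocol synopsis).
- Assumed randomised number: 151 − 80 = 71 up to 151 − 0 = 151, or about 36 to 75 per arm. The upper end assumes no roll-ins, although SAP Section 4 says they were used, so the true number should be lower than that.

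**Step 1: reproduce Table 5.** With n = 267/2 = 133.5 per arm and p̄ the mean of the two rates, power = Φ{[|p1 − p2|√n − 1.96√(2p̄(1 − p̄))] / √(p1q1 + p2q2)}. For 76% v 64% this is Φ{(1.387 − 1.270)/0.6425} = 0.572.

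| Contrast | Computed | Table 5 |
|---|---|---|
| Any AKI 76 v 64 | 0.572 | 0.57 |
| Any AKI 76 v 56 | 0.936 | 0.94 |
| Stage 2–3, 29 v 11 | 0.961 | 0.96 |
| Stage 2–3, 29 v 16 | 0.723 | 0.72 |

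The planned figures reproduce.

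**Step 2: power of Fisher's test at the assumed size.** Exact two-sided calculation: sum the binomial probabilities of all tables with p ≤ 0.05. This takes Fisher's test as applied to each dichotomy, because the SAP does not say which tables are tested.

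| Contrast | 36 per arm | 55 per arm | 75 per arm |
|---|---|---|---|
| Any AKI 76 v 64 | 14% | 22% | 30% |
| Stage 2–3, 29 v 16 | 18% | 29% | 41% |
| Any AKI 76 v 56 | 34% | 53% | 68% |
| Stage 2–3, 29 v 11 | 38% | 57% | 74% |

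**Step 3: what an overall interval would show.** If both arms have the control rate p, the half-width is 1.96√(2p(1 − p)/n).
- Any AKI: 1.96√(0.3648/75) = 13.7 points; 1.96√(0.3648/36) = 19.7 points.
- Stage 2–3: 1.96√(0.4118/75) = 14.5 points; 1.96√(0.4118/36) = 21.0 points.

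Against the Table 5 differences, with an observed difference of zero:
- Any AKI: 12 points is never excluded. 20 points is excluded clearly at 75 per arm and only just at 36.
- Stage 2–3: 13 points is never excluded. 18 points is excluded at 75 per arm but not at 36.

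**Step 4: the HCA = N row of SAP 6.9.** Assume two-thirds of those randomised are without HCA, the minimum share planned in Protocol 11.2. That is 47 to 101 patients, or n = 23.5 to 50.5 per arm. Under no effect the 95% limits are exp(±1.96√(2/(n p(1 − p)))).
- Any AKI: 0.40–2.49 at 101 patients, 0.26–3.81 at 47. Planned odds ratios are 0.56 and 0.40.
- Stage 2–3: 0.42–2.36 at 101 patients, 0.28–3.53 at 47. Planned odds ratios are 0.30 and 0.47.

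At 101 patients this row would exclude 0.30, would not exclude 0.56 or 0.47, and is borderline for 0.40. At 47 it would exclude none of the four.

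**Step 5: proportional odds.** Example 1 gives (0.64/0.36)/(0.76/0.24) = 0.56 for any AKI and (0.11/0.89)/(0.29/0.71) = 0.30 for Stage 2–3. A single common odds ratio does not describe that example well. Example 2 gives 0.40 and 0.47, which are closer together.

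**The case against.** Several stronger readings are tempting, and the documents do not support them.

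- *The report will contain nothing but p-values.* Not so. SAP 6.7.1.1 requires counts and proportions by arm in mutually exclusive stages, so a reader can derive a crude risk difference and interval. What is missing is pre-specification.
- *The trial cannot show whether it excluded the planned benefit.* This goes too far. The HCA = N row in SAP 6.9 gives an odds ratio with a 95% interval on both dichotomies, close to the population for which Table 5 was set. It is wide, unadjusted and labelled as a consistency check, but it exists.
- *Non-significance is the expected result even if the planned effect is real.* This holds for the two smaller effects across the whole range, and for all four at 36 per arm. It fails for the two larger effects at 55 and 75 per arm, where power is above one half.
- *A planned adjustment was dropped.* The protocol's primary test was itself unadjusted, and ANCOVA was for continuous endpoints. The creatinine stages are also defined relative to each patient's baseline.

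It is also fair to say that Table 5 shows example outcomes rather than a minimum worthwhile benefit, that nothing here biases the comparison, and that the SAP nowhere says it will read non-significance as no effect. These points limit the severity. They do not supply the missing overall estimate.

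**Conclusion.** The point holds in limited form and should be fixed. The SAP pre-specifies no overall effect estimate, no 95% interval and no adjustment for the primary comparison, and the protocol does not fill the gap. At 36 to 75 randomised per arm, Fisher power runs from 14% to 74% across the four Table 5 contrasts, so a non-significant result alone cannot distinguish no benefit from too few patients. An interval with a half-width of 13.7–19.7 points (any AKI) or 14.5–21.0 points (Stage 2–3) would show which of those differences remain open.

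This rests on the assumed randomised number, Table 5 control rates, equal arms and no missing stages. The gain in precision from adjustment is not established: it depends on how strongly baseline eGFR and HCA predict AKI stage, which the documents do not give.

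**What to change.** In SAP 6.7.1.1, beside the Fisher tests and for all randomised patients, add:

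1. The risk difference with 95% interval (for example Newcombe) for any AKI and for Stage 2–3.
2. A common odds ratio with 95% interval from an ordinal model adjusted for intended HCA and baseline eGFR, with the two dichotomous odds ratios beside it because Example 1 departs from proportional odds.
3. The same estimates for patients without HCA. Discuss the Table 5 differences against that interval, as context and not as a new decision rule.

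State the randomised number in each arm.

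The cost is a few sentences and a few standard model runs, with no new data. SAP Section 7 already provides for an amendment before analysis. The downside is a little extra output and reliance on a model assumption for the common odds ratio.
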